3 SYNOPSIS

[figure not shown]
Protocol Title	A Multicenter, Randomized, Double-blind, Placebo-controlled Study of the Safety and Efficacy of TS-121 as an Adjunctive Treatment for Patients with Major Depressive Disorder with an Inadequate Response to Current Antidepressant Treatment
Protocol Number	TS121-US201
Phase of Development	2a
Number of Study Sites	Approximately 25 US sites
Study Drug	TS-121: An oral, investigational new drug with antagonistic activity of the vasopressin 1b receptor (V _{1b} receptor)
Indication	Major Depressive Disorder (MDD)
Number of Patients	
Approximately 180 randomized male and female MDD patients between 18 and 65 years of age inclusive
 
 • Placebo Group: 60 patients • TS-121 10 mg Group: 60 patients • TS-121 50 mg Group: 60 patients
Objectives	
Primary Objectives
 
 • To evaluate the safety and tolerability of TS-121 compared to placebo in MDD patients • To evaluate the efficacy of two dose levels of TS-121 compared to placebo on MDD symptoms in MDD patients 
Exploratory Objective
 
 • To evaluate the effectiveness of biomarkers in predicting TS-121 response with retrospective stratification of patients via baseline values of HPA axis and inflammatory biomarkers
Safety assessments	
Safety and tolerability will be assessed from the time the patient is administered the investigational product through the final study procedure.
 
Safety variables for assessment will include:
 
 • Adverse events • Physical examination • Columbia Suicide Severity Rating Scale (C-SSRS) • Body weight • Vital signs

	
 • Clinical laboratory tests (hematology, biochemistry and urinalysis) • 12-lead electrocardiogram (ECG) • Ophthalmological examinations
Efficacy assessments	
Primary Endpoint
 
 • Change in MADRS total score from Visit 3 (Baseline) to Visit 6 (EOT) 
Secondary Endpoints
 
 • Changes from Visit 3 (Baseline) to Visit 6 (EOT) for CGI-S, SDQ, and HAM-A total scores • Percentage of CGI-I improvers (“Very much improved” or “Much improved”) • Percentage of MADRS responders ($\geq 50\%$ reduction in total score)

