^e Investigational product dispensing, accountability and compliance checks: Accountability and compliance checks will be performed at Visits 3 to 6. Administration of the investigational product for the placebo lead-in period will start on the morning following Visit 2 (study Day 2). Administration of the investigational product for the treatment period will start on the morning following Visit 3 (study Day 16).

^f Drug Adherence: Daily dosing by patients of current ADT and investigational product (TS-121 or placebo) will be monitored using AiCure technology on the patient's smart phone or a device provisioned by the site (See Section 8.1.3, Treatment Compliance).

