9.2.4 Medical History

A detailed medical and/or surgical history will be obtained by the investigator or qualified designee and will be recorded in the patient's study source records and captured electronically. Medical history should include information on hepatic, renal, gastrointestinal, and cardiovascular disorders, eye disease, and/or any other clinically significant medical condition. New or existing medical conditions reported prior to first administration of the investigational product will be captured as medical history, whereas any new, untoward, or worsening medical condition reported after first administration of the investigational product will be captured as adverse events.

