9.2.7.4 Ophthalmological Examination

Ophthalmological examinations will be performed on all patients at the visits indicated in Section 9.1. The Lens Opacities Classification System III (LOCS III) grading must be conducted by an ophthalmologist, with active certification for LOCS III grading. The Best Corrected Visual Acuity (BCVA) measurement must be conducted by the ophthalmologist, optometrist or a trained ophthalmic technician. LogMAR score should be confirmed by the ophthalmologist. Rating by the same ophthalmologist, optometrist or a trained ophthalmic technician and same equipment is preferred for the duration of the trial for each patient for the LOCS III grading and the BCVA measurement. Ophthalmological examination will include the following:

- BCVA as measured with the ETDRS chart, and scored in LogMAR
- Evaluation of the crystalline lens through a maximally dilated pupil using LOCS III, including the following features;
 - Posterior subcapsular cataract (P)
 - Cortical cataract (C)
 - Nuclear opalescence (NO)
 - Nuclear color (NC)

Examination of the anterior chamber depth, optic nerve head, and the intraocular pressure by applanation tonometry should be performed by the ophthalmologist prior to dilation of pupils. Mydriatics will be used to achieve maximal mydriasis before any retro illumination or slit lamp photographs are obtained. Photographs of both eyes will be captured on all patients at each examination. The ophthalmologist should not review the previous LOCS III assessments until completion of the LOCS III assessment of a current visit.

(See the Ophthalmological Examination Manual for detailed instructions).

Results of the ophthalmological examination will be recorded in the patient's study source records and captured electronically. Any of clinically significant ophthalmological findings defined in Section 11.3.2 will be recorded as AEs. The sponsor will engage a third-party blinded ophthalmologist to review clinically significant ophthalmological findings or consult with the investigators or sponsor Medical Monitor.

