9.3 Visit and Time Windows

Visit and time windows for each visit are summarized in Section 9.1. Visit 1 can be performed from Day -28 to Day -7, and must be performed prior to Visit 1.1. Visit 1.1 can be performed from Day -13 to Day -2. Visit 2.1 has a ±2 day window. Visit 3 has a +3 day window and must be performed after obtaining results for Visit 2.1. All visits after Visit 3 will have a visit window of ±3 days. The ophthalmological examination at Visit 2 can be performed within -5 days of

study Day 1 (Day -5 to Day 1).

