11 ADVERSE EVENT REPORTING

11.1 Definitions, Grading & Relationship, Outcome and Follow-up

11.1.1 Definitions

Adverse Event (AE): Any untoward medical occurrence in a patient administered an investigational product, and which does not necessarily have a causal relationship to investigational product. An AE can be any unfavorable or unintended sign (including an abnormal finding), symptom, or disease. AEs include any occurrence that is new in onset or aggravated in severity or frequency from the baseline condition, or abnormal results of diagnostic procedures (including clinically-significant laboratory test abnormalities). Overdose defined in Section 11.6.1 will also be considered as an AE whether or not it is associated with symptoms or abnormal laboratory results.

Events should be considered AEs if they:

- result in discontinuation from the study,
- require treatment or any other therapeutic intervention,
- require further diagnostic evaluation (excluding a repetition of the same procedure to confirm the abnormality),
- are associated with clinical signs or symptoms judged by the investigator to have a significant clinical impact.

Appropriate therapeutic action and follow-up measures will be performed by the investigator in accordance with GCP. These actions and measures will continue until the condition is resolved and/or the etiology is identified. Any non-serious AEs (including laboratory results or other clinical findings) that result in the patient's withdrawal from the study will require the patient to undergo early discontinuation procedures.

Laboratory Abnormalities: It is the responsibility of the investigator to review all laboratory findings for all patients. Abnormal values should be commented upon as to clinical relevance or importance in the study source records or the laboratory report as appropriate. An abnormal laboratory value may be considered an adverse event if the identified laboratory abnormality leads to any type of intervention whether prescribed in the protocol or not. Medical and scientific judgment should be exercised in deciding whether an isolated laboratory abnormality should be classified as an adverse event.

All laboratory abnormalities considered to constitute an adverse event should be reported on the appropriate section of the patient's study source records. Laboratory abnormalities do not need to be listed as separate adverse events if they are considered to be part of a clinical

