- If a death occurs and an autopsy is performed, a copy of the autopsy report should be obtained if possible when it becomes available. All efforts must be undertaken to obtain follow-up information promptly.

Any SAEs occurring from first administration of investigational product through 30 days after last administration must be reported. All SAEs will be reported, whether or not they are deemed to be related to study product. Timely reporting of SAEs will be followed in accordance with regulatory requirements as outlined in the Safety Plan.

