## **6.1.3.1 Adverse Events**

An adverse event (AE) is defined as any untoward medical occurrence in a patient administered an investigational product, and which does not necessarily have a causal relationship to investigational product. An AE can be any unfavorable or unintended sign (including an abnormal finding), symptom, or disease. AEs include any occurrence that is new in onset or aggravated in severity or frequency from the baseline condition, or abnormal results of diagnostic procedures (including clinically significant laboratory test abnormalities). AEs also include an intentional or accidental overdose, whether or not it is associated with symptoms. An overdose is defined as ingestion of the investigational product (accidental or intentional) more than 3 capsules in the same calendar day.

AEs will be recorded after the first administration of the investigational product in the placebo lead-in period through follow-up. AEs with onset date and time (if available) after the first administration of randomized treatment will be considered treatment emergent AE (TEAE).

Any AEs with incomplete start and end dates/times will be treated as follows:

- Adverse events with unknown start and/or end times (but where the date is known) will be imputed as post-dose for events on first treatment day of placebo lead-in or randomized treatment or with a time of 00:00 for other days. The missing time will be shown blank in the listings.
- Adverse events with incomplete start day and known month will be imputed as the later of: day of first placebo lead-in dose or first randomized dose started in that month or first of the month. Missing day will be printed -- in the listings.
- Adverse events with incomplete start dates missing month and day will be considered as the later of: day of first placebo lead-in dose or first randomized dose started in that year or January 1. Missing month and day will be printed ----- in the listings.
- Adverse events with completely unknown start dates will be considered as treatment emergent for the tabulations and the missing dates will be shown as ----- in the listings.

Details of AE classification for severity (mild, moderate or severe), action taken and relationship to test drug (not related, possibly related, probably related and definitely related) are provided in Appendix C. All AEs will be coded using MedDRA Version 19.1.

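### The text starts AE and SAE collection at the first lead-in capsule on Day 2, so harm from required earlier procedures, such as the dilated eye examination, has no AE or SAE route

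*Protocol*

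**What the plan says.** **When collection starts.** Protocol 11.2.2 sets the SAE window: "Any SAEs occurring from first administration of investigational product through 30 days after last administration must be reported". SAP 6.1.3.1 sets the AE window: "AEs will be recorded after the first administration of the investigational product in the placebo lead-in period through follow-up". The Protocol synopsis agrees: "Safety and tolerability will be assessed from the time the patient is administered the investigational product through the final study procedure". SAP 6.1.3 starts safety assessment at the lead-in placebo in the same way. The AE definition in Protocol 11.1.1 is also tied to dosing: "Any untoward medical occurrence in a patient administered an investigational product".

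**When the first dose is.** Footnote e of Protocol 9.1 states: "Administration of the investigational product for the placebo lead-in period will start on the morning following Visit 2 (study Day 2").

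**What happens to earlier events.** Protocol 9.2.4 states: "New or existing medical conditions reported prior to first administration of the investigational product will be captured as medical history". Section 9.2.5 says the same for psychiatric conditions, and 9.2.7.2 and 9.2.7.3 for abnormal physical and neurological findings. SAP 6.1.1 and 6.1.3.6 repeat the rule.

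**What is done before the first dose.** Visit 1 (Day -28 to Day -7) includes blood sampling and a 12-lead ECG. The Visit 2 eye examination may be done early: "The ophthalmological examination at Visit 2 can be performed within -5 days of" Day 1 (Protocol 9.3). It includes applanation tonometry, and Protocol 9.2.7.4 adds: "Mydriatics will be used to achieve maximal mydriasis before any retro illumination or slit lamp photographs are obtained".

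**What points the other way.** The schedules in Protocol 9.1 and SAP Table 1 start the AE inquiry row at Visit 2, Day 1. Protocol 11.3 and 11.3.1 require suicidal ideation and behavior to be recorded as an AE and reported within 24 hours, with no stated start date.

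**The concern.** Every patient entering the lead-in has procedures done only because of the trial before AE and SAE collection opens in the text. If one of them causes harm, the plan files it as a condition the patient brought to the study. An investigator following 11.2.2 has no obligation to send a 24-hour report, however serious the event.

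The eye examination shows this most clearly. It is repeated at Visits 5, 6 and 7 and at early termination, where a reaction to dilation would be an AE. The same reaction at Visit 2 would be history.

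The Visit 2 examination also decides eligibility: exclusion criterion 20 removes patients on their LOCS III grades. Some patients may therefore be dilated and never dosed, and events in those patients are the least visible of all. Safety is a primary objective, and a procedure problem at the first examinations would not reach the sponsor through the trial's own reporting channel.

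**Working it through.** The plan gives no figure to reproduce. The check is a day count, followed by a comparison of the passages.

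**1. Days from procedure to first capsule (Day 2).** The visit windows come from Protocol 9.1 and 9.3. The documents do not say whether a Day 0 exists, so both counts are shown. For a procedure on Day -d, the gap is d + 2 - 1 without a Day 0 and d + 2 with one.

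| Procedure | Day | No Day 0 | With Day 0 |
|---|---|---|---|
| Visit 1, earliest | -28 | 28 + 2 - 1 = 29 | 28 + 2 = 30 |
| Visit 1, latest | -7 | 7 + 2 - 1 = 8 | 7 + 2 = 9 |
| Eye examination, earliest | -5 | 5 + 2 - 1 = 6 | 5 + 2 = 7 |
| Eye examination, latest | 1 | 2 - 1 = 1 | 2 - 1 = 1 |

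Visit 1 procedures fall 8 to 30 days before the written window opens, and the eye examination 1 to 7 days before. No permitted timing of the Visit 2 examination falls inside the window.

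**2. Does the schedule row close the gap?** If the row starting AE inquiry at Visit 2 governed, Day 1 would be covered. Visit 1 procedures, and eye examinations done on Day -5 to Day -1, would still be outside.

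**3. Does the lens-opacity rule close it?** No. Under Protocol 11.3.2 a Class I lens event is an increase from baseline, and the section's other trigger is also a change. SAP 6.3.16.6 takes the Visit 2 examination as that baseline, so the first examination cannot produce a Class I event.

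**4. Where would the event appear?**
- *Patient later dosed:* in the medical and psychiatric history listing and table (SAP 6.3.11.4, Listing 16.2.4.3 and Table 14.1.4). If it worsens after the first dose, it becomes an AE (Protocol 9.2.4 and 9.2.5).
- *Patient who leaves before Day 2:* outside the safety analysis population, which requires at least one dose (Protocol 10.2, SAP 6.2.1). The AE and history outputs are restricted to that population. The disposition listing covers all screened patients, but its entry for a screen failure is a date and a primary reason (SAP 6.3.9).

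**5. How many patients could be in the second group?** Protocol 7.1 plans about 300 screened and about 180 randomized, so about 300 - 180 = 120 are not randomized. The documents do not say how many of these stop before Day 2, so the range is 0 to about 120.

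**6. Suicidal ideation and behavior.** Section 9.2.5 sends new pre-dose psychiatric conditions to history. Section 11.3.1 requires an AE record and a 24-hour report without saying from when. For an event during screening, the two sections give different instructions.

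**The case against.** The strongest case for leaving the plan alone is that a first-dose start is a deliberate and consistent choice, repeated across protocol and SAP. The safety objective compares TS-121 with placebo, and events before any capsule cannot bear on that. Later eye examinations fall inside AE collection, so a recurring procedure problem would surface there. Glaucoma and previous eye surgery are excluded, and chamber depth and pressure are examined before dilation. The harm is hypothetical, and a Safety Plan not among these documents may add reporting detail.

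Most of this stands, and it limits the weight of the point. It does not supply a route for harm that occurs before dosing.

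A reader might also infer more than the documents support:
- *That such harm is never captured.* For patients later dosed it is captured electronically, listed and tabulated as history. What is missing is the AE or SAE label and the expedited report.
- *That nothing is asked before Day 2.* The schedule starts AE inquiry on Day 1. This is an inconsistency between table and text.
- *That a suicide attempt during screening would go unreported.* Section 11.3.1 can be read as requiring a 24-hour report. The finding there is a contradiction, not a clear gap.
- *That barring certain drug classes from Visit 1 adds trial-imposed harm.* Patients treated with drugs that might influence the HPA axis are excluded (criterion 13), and no passage directs that a drug be withdrawn for entry.
- *That the AE definition in 11.1.1 is itself the defect.* It sets no dates. Section 11.2.2 sets the SAE window.

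**Conclusion.** The point holds in a limited form. Under the text of both documents, harm from a required procedure before Day 2 is filed as history and has no AE or SAE route. The uncovered period is 8 to 30 days from Visit 1 and 1 to 7 days from the eye examination, and it applies to every patient who enters the lead-in. In patients who leave before Day 2 (0 to about 120), the event appears in no safety or history output.

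Two conflicts must be reconciled whatever the sponsor decides about the window: the Day 1 schedule row against the Day 2 text, and 9.2.5 against 11.3.1.

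The conclusion assumes that the unseen Safety Plan does not already extend reporting back to consent. The documents give no event frequency; it is expected to be low. No treatment comparison or treatment-emergent AE table is affected. The change is worth making because trial-caused harm is misfiled and the remedy is cheap, not because many events are likely.

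**What to change.** Anchor the change in Protocol 11.2.2. State that all SAEs, and any AE the investigator attributes to a study procedure, are recorded and reported from informed consent. Keep the history rule for other conditions before the first dose.

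- Add a CRF field for relationship to study procedure. The present causality scale (Protocol 11.1.2, SAP Appendix C) covers test drug only.
- List these events for all consented patients as pre-treatment events, outside the lead-in AE and treatment-emergent AE tables.
- Align the AE inquiry row in both schedules, the synopsis, Protocol 9.2.4, 9.2.5, 9.2.7.2, 9.2.7.3 and 11.1.1, and SAP 6.1.1, 6.1.3, 6.1.3.1 and 6.1.3.6. Changing only some of these would create new contradictions.
- Reconcile Protocol 9.2.5 with 11.3.1, so that a site has one instruction for suicidal ideation or behavior before the first dose.

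The cost is a few extra reports, one CRF field, one short listing and wording changes in both documents.

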11.1.2 Grading and Relationship

The investigator will evaluate all AEs as to their severity, and record the outcome and action taken. The investigator will also judge the likelihood that the AE was related to the investigational product and document this in the patient's study source records. See Table 4 below:

Table 4. Classification of Adverse Events

Severity	Mild	awareness of sign or symptom, but easily tolerated
	Moderate	discomfort enough to cause interference with usual activity
	Severe	incapacitating with inability to work or do usual activity
Duration	Record the start and stop dates of the adverse experience. If less than 1 day, indicate the appropriate length of time and units	
Action taken	Did the adverse experience cause the test drug to be discontinued? Interrupted? Dosage increased or decreased? Other action?	
Relationship to test drug	Did the test drug cause the adverse experience? The determination of the likelihood that the test drug caused the adverse experience will be provided by an investigator. The investigator's signed/dated initials on the source document supporting the causality noted on the AE form ensures that a medically qualified assessment was done. This initialed document must be retained for the required regulatory time frame. The criteria below are intended as reference guidelines to assist the investigator in assessing the likelihood of a relationship between the test drug and the adverse experience based upon the available information. The greater the correlation with the components and their respective elements (in number and/or intensity), the more likely the test drug caused the adverse experience:	
	Exposure	Is there evidence that the patient was actually exposed to the test drug such as: reliable history, acceptable compliance assessment (pill count, diary, etc.), expected pharmacologic effect, or measurement of drug/metabolite in bodily specimen?
	Time Course	Did the AE follow in a reasonable temporal sequence from administration of the test drug? Is the time of onset of the AE compatible with a drug-induced effect?
	Likely Cause	Is the AE not reasonably explained by another etiology such as underlying disease, other drug(s)/vaccine(s), or other host or environmental factors?
	Dechallenge	Was the dose of test drug discontinued or reduced? If yes, did the AE resolve or improve? If yes, this is a positive dechallenge. If no, this is a negative dechallenge. (Note: This criterion is not applicable if: (1) the AE resulted in death or permanent disability; (2) the AE resolved/improved despite continuation of the test drug; or (3) the study is a single-dose drug study.)
	Rechallenge	Was the patient re-exposed to the test drug in this study? If yes, did the AE recur or worsen? If yes, this is a positive rechallenge. If no, this is a negative rechallenge. (Note: This criterion is not applicable if: (1) the initial AE resulted in death or permanent disability, or (2) the study is a single-dose drug study.)
	Consistency with Investigational Product Profile	Is the clinical/pathological presentation of the AE consistent with previous knowledge regarding the test drug or drug class pharmacology or toxicology?
	The assessment of relationship will be reported on the case report forms/worksheets by an investigator according to his/her best clinical judgment, including consideration of the above elements. Use the following scale of criteria as guidance (not all criteria must be present to be indicative of a drug relationship).	
	Definitely related	A clinical event, including laboratory test abnormality, occurring in a plausible time relationship to drug administration, and which cannot be explained by concurrent disease or other drugs or chemicals. The response to withdrawal of the drug (dechallenge) should be clinically plausible. The event must be definitive pharmacologically or phenomenologically, using a satisfactory

	rechallenge procedure if necessary.
Probably related	A clinical event, including laboratory test abnormality, with a reasonable time sequence to administration of the drug, unlikely to be attributed to concurrent disease or other drugs or chemicals, and which follows a clinically reasonable response on withdrawal (dechallenge). Rechallenge information is not required to fulfil this definition.
Possibly related	A clinical event, including laboratory test abnormality, with a reasonable time sequence to administration of the drug, but which could also be explained by concurrent disease or other drugs or chemicals. Information on drug withdrawal may be lacking or unclear.
Not related	A clinical event, including laboratory test abnormality, with a temporal relationship to drug administration which makes a causal relationship improbable, and in which other drugs, chemicals or underlying disease provide plausible explanations.

